8.2.5.1. Hepatic Safety Electronic Case Report Form

This table describes when additional hepatic safety data collection in the hepatic safety eCRF should be done.

If a participant with baseline...	has the following elevations...
ALT <1.5 × ULN	ALT ≥5 × ULN on 2 or more consecutive blood tests
ALP <1.5 × ULN	ALP ≥2 × ULN on 2 or more consecutive blood tests
TBL <1.5 × ULN	TBL ≥2 × ULN, except for cases of known Gilbert's syndrome
ALT ≥1.5 × ULN	ALT ≥3 × baseline on 2 or more consecutive blood tests
ALP ≥1.5 × ULN	ALP ≥2 × baseline on 2 or more consecutive blood tests
TBL ≥1.5 × ULN	TBL ≥2 × baseline

Abbreviations: ALP = alkaline phosphatase; ALT = alanine aminotransferase; AST = aspartate aminotransferase; TBL = total bilirubin; ULN = upper limit of normal.

Note: The interval between the 2 consecutive blood tests should be at least 2 days.

Additional criteria include

- a hepatic event considered to be an SAE, and
- discontinuation of study intervention due to a hepatic event (Section 7.1).

8.2.6. Suicidal Ideation and Behavior Risk Monitoring

Participants should be monitored appropriately and observed closely for suicidal ideation and behavior or any other unusual changes in behavior, especially at the beginning and end of the course of intervention. Consideration should be given to discontinuing the study intervention in participants who experience signs of suicidal ideation or behavior, following a risk assessment.

Suicidal ideation and behavior will be monitored using the C-SSRS and self-harm forms.

C-SSRS and Self-Harm Forms

The C-SSRS is a scale that captures the occurrence, severity, and frequency of suicidal ideation and behavior during the assessment period via a questionnaire. The scale was developed by the National Institute of Mental Health (NIMH) trial group as a counterpart to the Columbia Classification Algorithm of Suicide Assessment (CCASA) categorization of suicidal events.

For this study, the C-SSRS is adapted for the assessment of the ideation and behavior categories only. The Intensity of Ideation and Lethality of Behavior sections are removed.

The C-SSRS is currently referenced by the US Food and Drug Administration (FDA) (Guidance 2012) as an acceptable scale and is used in clinical trials for neuroscience and non-neuroscience compounds. The C-SSRS is included in the master protocol because prospective collection of suicidal thoughts and behaviors is recommended for compounds reviewed by the FDA's Division of Anesthesiology, Addiction Medicine, and Pain Medicine, as there is often an enhanced risk of depression in the populations under study. As noted in the FDA guidance, prospective questioning will help avoid misclassification of suicidal thoughts and behaviors and ensure that participants who are experiencing suicidal thoughts and behaviors are properly recognized and adequately treated.

The self-harm forms focus only on suicidal and nonsuicidal self-harm behaviors. The Self-Harm Supplement form is a single-question. If a self-harm event is identified, investigators will then complete the Self-Harm Follow-Up form, which provides a description of the behavior.

8.3. Adverse Events and Serious Adverse Events

Adverse events will be reported by the participant (or, when appropriate, by a caregiver, surrogate, or the participant's legally authorized representative).

The investigator and any qualified designees are responsible for detecting, documenting, and recording events that meet the definition of an AE or SAE and remain responsible for following up AEs that are serious, that are considered related to the study intervention or study procedures, or that caused the participant to discontinue participation (see Section 7).

8.3.1. Time Period and Frequency for Collecting AE and SAE Information

All SAEs will be collected from the start of intervention until the follow-up visit.

All AEs will be collected from the signing of the ICF for the master protocol until participation in an ISA or the master protocol has ended, whichever is longest.

Medical occurrences that begin before the start of study intervention but after signing of the ICF will be recorded on the AE CRF.

Although all AEs that occur after signing of the ICF are recorded by the site in the CRF or by electronic data entry, SAE reporting to sponsor begins after the participant has signed the ICF and has received study intervention.

If an SAE occurs after signing of the ICF, but prior to receipt of study intervention, then it needs to be reported ONLY if it is considered reasonably possibly related to study procedures.

All SAEs will be recorded and reported to the sponsor or designee immediately, and under no circumstance should this exceed 24 hours, as indicated in Appendix 3, Section 10.3. The investigator will submit any updated SAE data to the sponsor within 24 hours of it being available.

Investigators are not obligated to actively seek AEs or SAEs after conclusion of the ISA participation. However, if the investigator learns of any SAE, including a death, at any time after a participant has been discharged from the study, and he/she considers the event to be reasonably related to the study intervention or study participation, the investigator must promptly notify the sponsor.

8.3.2. Method of Detecting AEs and SAEs

The method of recording, evaluating, and assessing causality of AEs and SAEs and the procedures for completing and transmitting SAE reports are provided in Appendix 3.

Care will be taken not to introduce bias when detecting AEs and/or SAEs. Open-ended and nonleading verbal questioning of the participant is the preferred method to inquire about AE occurrences.

8.3.3. Follow-Up of AEs and SAEs

After the initial AE/SAE report, the investigator is required to proactively follow each participant at subsequent visits/contacts. All SAEs will be followed until resolution, stabilization, the event is otherwise explained, or the participant is lost to follow-up (as defined in Section 7.3). Further information on follow-up procedures is provided in Appendix 3, Section 10.3.

8.3.4. Regulatory Reporting Requirements for SAEs

Prompt notification by the investigator to the sponsor of an SAE is essential so that legal obligations and ethical responsibilities towards the safety of participants and the safety of a study intervention under clinical investigation are met.

The sponsor has a legal responsibility to notify both the local regulatory authority and other regulatory agencies about the safety of a study intervention under clinical investigation. The sponsor will comply with country-specific regulatory requirements relating to safety reporting to the regulatory authority, Institutional Review Boards (IRBs)/Independent Ethics Committees (IECs), and investigators.

An investigator who receives an investigator safety report describing an SAE or other specific safety information (for example, summary or listing of SAEs) from the sponsor will review and then file it along with the IB and will notify the IRB/IEC, if appropriate according to local requirements.

8.3.5. Pregnancy

Details of all pregnancies will be collected in female participants and, if indicated in each ISA, female partners of male participants. The time period for collecting pregnancy information will be detailed in each ISA as applicable.

If a pregnancy is reported, the investigator should inform the sponsor within 24 hours of learning of the pregnancy and should follow the procedures outlined in Appendix 4, Section 10.4.

Abnormal pregnancy outcomes (for example, spontaneous abortion, fetal death, stillbirth, congenital anomalies, ectopic pregnancy) are considered SAEs.

8.3.6. Complaint Handling

Lilly collects product complaints on interventions used in clinical studies to ensure the safety of study participants, monitor quality, and facilitate process and product improvements.

Participants will be instructed to contact the investigator as soon as possible if they have a complaint or problem with an intervention so that the situation can be assessed.

8.4. Treatment of Overdose

In the event of an overdose, the investigator should

1. contact the Medical Monitor immediately
2. closely monitor the participant for any AEs/SAEs and laboratory abnormalities, and
3. document information about the overdose as specified in the ISA.

Decisions regarding dose interruptions or modifications will be made by the investigator in consultation with the Medical Monitor based on the clinical evaluation of the participant.

Additional guidance for the treatment of overdose will be described in the ISA as applicable.

8.5. Pharmacokinetics

Pharmacokinetic parameters may be evaluated in the ISAs governed by this protocol. Information on pharmacokinetic sample collection and parameter analysis will be described in the ISA as applicable.

Sample retention is described in Section [10.1.12](#).

8.6. Pharmacodynamics

Pharmacodynamic parameters may be evaluated in the ISAs governed by this protocol. Information on pharmacodynamic sample collection and parameter analysis will be described in the ISA as applicable.

Sample retention is described in Section [10.1.12](#).

A large, stylized graphic consisting of the letters 'C', 'C', and 'I' in a bright red color. The letters are thick and have a slightly irregular, hand-drawn appearance. They are set against a solid black rectangular background that occupies the lower half of the page.

The image shows the letters 'CCI' in a large, bold, red, sans-serif font. The letters are set against a solid black rectangular background. The 'C's are slightly open at the top and bottom, and the 'I' is a simple vertical bar.

8.9. Immunogenicity Assessments

Immunogenicity may be evaluated in the ISAs governed by this protocol. Information on immunogenicity sample collection and assessments will be described in the ISA as applicable.

See Section [10.1.12](#) for sample retention information.

8.10. Health Economics

The EQ-5D-5L is a quality of life assessment that can provide information for health economics assessments.

9. Statistical Considerations

9.1. Statistical Hypotheses

For each ISA in this master protocol, a Bayesian critical success factor (CSF) will be defined in the ISA and used to evaluate whether the ISA met its primary endpoint. The CSF will be evaluated for the primary efficacy endpoint, average pain intensity as measured by the NRS, using the methodology described in Section 9.4.2 and will be calculated at the conclusion of the double-blind portion of each ISA within the master protocol.

The CSF will have the general form of:

- probability (treatment effect < effect of interest) > probability threshold.

The treatment effect will be defined as the LY estimate–placebo estimate of the change from baseline at endpoint. The effect of interest is typically found through a literature search or clinical judgement. The probability threshold is generally set to have a desired level of confidence in the treatment effect or to have the desired operating characteristics under a range of plausible, assumed drug effect scenarios of truth, including a null effect.

Additional hypotheses will include the comparison of each active intervention with placebo for the prespecified objectives and endpoints defined in Section 3.

9.2. Sample Size Determination

The sample size, power, and false positive rate for each ISA within the master protocol will be provided and justified in the ISA.

The sample size and operating characteristics of each ISA within the master protocol will be evaluated by simulation. The simulations will include various assumed effect sizes and/or treatment differences and prior distribution specifications. Also provided will be a justification of how missing data are accounted for, if and how placebo or treatment-effect information is borrowed from other ISAs, and other key information needed to conduct a simulation study. Both sample size and operating characteristics may vary by ISA. The false positive rate is defined as the percentage of times the CSF is met, assuming that the treatment effect is 0 at all postbaseline visits and may vary by ISA.

An ISA that enters the master protocol later in calendar time may potentially randomize fewer participants, since there may be a bolus of placebo participants or treatment-effect information that can be borrowed and used in the primary efficacy analysis. Operating characteristics may also vary for the ISAs that enter later in calendar time for the same reason.

Each ISA will randomize to both the active intervention(s) and placebo CCI
Multiple intervention arms may be included in the ISA CCI

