4.2. Scientific Rationale for Study Design

The master protocol construct will

- offer flexibility to continually add different interventions at different time points across different participant populations
- enable efficient testing of multiple promising targets across multiple pain states
- allow direct statistical comparisons of interventions studied within a pain type
- enable borrowing of
 - placebo participants within a pain type, and
 - treatment-effect information across pain types for a given intervention
- facilitate smaller ISA sample sizes as the trial progresses due to the ability to borrow placebo and treatment-effect information
- provide potential site benefit based on multiple therapies offered, and
- offer continuous screening of participants for future interventions.

The proposed design provides many unique operational and statistical challenges as well as opportunities to make the best decisions in advancing molecules through the drug development process.

The primary efficacy analysis is a Bayesian mixed-model repeated measures (MMRM) method that allows the borrowing of placebo information within a DSA and borrowing of treatment difference information between different addendum pain types. The amount of borrowing and the statistical methodology used to accommodate the borrowing (for example, pooling of data, hierarchical modeling), including the specifics of the Bayesian prior distributions, will be specified within each ISA.

The master protocol also allows for adaptations specified within an ISA. The adaptations may include stopping for early futility, stopping for early efficacy, sample size re-estimation, or removal of a dose arm.

Intervention-specific design elements are described in the respective ISA.

Efficacy Assessments

The master protocol contains a core set of assessments based on the Initiative on Methods, Measurement, and Pain Assessment in Clinical Trials (IMMPACT) guidelines (Dworkin et. al. 2005). The recommended domains when designing chronic pain clinical studies are

- pain
- physical functioning
- emotional functioning
- participant ratings of overall improvement
- adverse events (AEs), and
- participant disposition.

The NRS was selected for the primary endpoint based on its demonstrated ability to detect changes in pain and its common use across the disease states under study.

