5.4.1. Participation in Multiple ISAs

Interested participants will have the opportunity to participate in multiple ISAs within the same disease state or for different disease states.

Participation in multiple ISAs is allowed if the participant

- meets all inclusion or exclusion criteria for the master protocol, the applicable DSA, and the respective ISA at the time of screening
- has not participated in another ISA with the same intervention
- has completed the 30-day waiting period since participating in another clinical study involving an intervention
 - EXCEPTION – if the participant did not receive intervention, then the participant does not need to complete the 30-day waiting period

- has completed all previous ISAs without early discontinuation
 - EXCEPTION – if the participant discontinues without receiving intervention.

The intervention that the participant received in a previous ISA will have no impact on the randomization of treatment to the current ISA. The number of participants who will participate in multiple ISAs is unknown. Participation in more than one ISA, referred to as 'repeat participation,' will be tracked at the site level, the ISA level, and at the overall master protocol level.

Repeat participation may introduce the potential concern that populations between ISAs may be too homogenous or introduce potential biases into the participant population for future ISAs, such as inflation or deflation of placebo response in repeat participants, or bias of completers in the data set. If these issues occur, edits will be made to future amendments of the Master Protocol or an ISA to address this concern.

6. Study Intervention

Study intervention is defined as any investigational intervention(s), marketed product(s), placebo, or medical device(s) intended to be administered to a study participant according to the study protocol.

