9.4.2.1. Key Features of the Bayesian Primary Efficacy Analysis Model

The primary efficacy analysis will be a Bayesian longitudinal MMRM analysis conducted on the NRS average pain score. The model will include the categorical effects and covariates described in Section 9.4.2. The change from baseline to each postbaseline time interval will be assessed.

The primary efficacy analysis model includes these key features:

- ability to borrow placebo information from other ISAs within the DSA using a suitable choice of informative prior on the key parameters
- ability to borrow treatment-effect information from other ISAs between DSA for the same intervention using a suitable choice of informative prior on the key parameters
- ability to update and tune the model parameters as more ISAs are added to the master protocol and more data become available
- flexibility for each ISA to define the amount of borrowing that will occur by specifying the prior distributions of key parameters in the ISA SAP
- ability to define which data from additional ISAs are included in the model
- flexibility to include additional covariates for each ISA as needed, and
- option to specify informative priors on some model parameters based on external data sources, for example, utilization of Bayesian Augmented Control for placebo parameters and data to inform other key parameters.

The ISA SAP will contain the exact specification of the model and parameters for the respective ISA.

Borrowing Strategy

Each ISA will define the specific decisions on the borrowing of placebo and treatment-effect information, including if borrowing will be implemented and, if so, how much information to borrow and the specific methodology used to borrow. These decisions may vary over the course of the master protocol, as some borrowing strategies may perform better than others as more data are available to borrow.

Specific differences between ISAs, for example, method of administration or additional inclusion or exclusion criteria, may impact the borrowing strategy for an ISA. Adjustments may also be made to the primary analysis model to incorporate the difference in placebo response in different time periods to facilitate efficient borrowing between the placebo participants.

The current borrowing strategies considered across the master protocol for each ISA include

- pooling of placebo data between ISAs within a disease state

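### Does Section 9.2 need a wider definition of the false positive rate for ISAs that borrow placebo or treatment-effect information?

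*Protocol*

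**What the plan says.** Protocol Section 9.2 leaves the sample size, power and false positive rate to each ISA, to be supplied and justified there from simulation. It gives one general definition: the rate is "defined as the percentage of times the CSF is met, assuming that the treatment effect is 0 at all postbaseline visits". On what the simulations vary, it says "The simulations will include various assumed effect sizes and/or treatment differences and prior distribution specifications". Each ISA must also justify "if and how placebo or treatment-effect information is borrowed from other ISAs", along with the handling of missing data and whatever else a simulation needs. The section adds that the operating characteristics of later ISAs may differ because of borrowing.

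Section 9.1 says the probability threshold in the critical success factor (CSF) may be chosen for a wanted level of confidence, or for operating characteristics "under a range of plausible, assumed drug effect scenarios of truth, including a null effect".

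Borrowing is central to the design. Section 4.2 expects it to "facilitate smaller ISA sample sizes as the trial progresses due to the ability to borrow placebo and treatment-effect information", and Section 9.2 says "An ISA that enters the master protocol later in calendar time may potentially randomize fewer participants". Section 9.4.2.1 lists six strategies, from pooling placebo to using the ISA's own data only, and each ISA makes the choice. The protocol also recognises that placebo response may not be stable. Section 9.4.2.1 says "Adjustments may also be made to the primary analysis model to incorporate the difference in placebo response in different time periods", and Section 5.4.1 mentions "inflation or deflation of placebo response in repeat participants".

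**The concern.** With borrowing, the chance that an inactive drug meets the CSF depends on more than its own zero effect. If borrowed placebo participants improved less than concurrent ones would have, the comparator looks worse and the drug looks better. If they improved more, the reverse happens. If treatment effects are borrowed across disease states, an intervention that works in the donor states pulls up the estimate in a state where it does not work.

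Section 9.2 names neither quantity. It does not say whether the zero effect also holds in the donor ISAs, and none of the factors it lists for simulation is a placebo difference. Read literally, an ISA could report only the case with no placebo difference and inactive donors. Because borrowing is also the reason later ISAs may be smaller, that one value could misstate the error rate, in either direction, when sample size and threshold are being chosen. The sensitivity analyses of borrowing in Section 9.4.8 come after the data are in and cannot inform that choice.

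**Working it through.** The protocol gives no false positive rate, sample size, SD or CSF number, so there is no figure to reproduce. Every input below is an assumption, used only to see whether the dependence exists and how large it could be.

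**Assumed inputs.** SD of change 2.2 NRS points; 100 active (nT); 50 concurrent placebo (nC); 100 borrowed placebo (nB); CSF met if Pr(effect < 0) > 0.95, so z = 1.645; flat priors; true effect in the ISA equal to 0. Let d be the number of points by which borrowed placebo improved less than concurrent placebo.

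**Pooled placebo.**

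- SE = SD × √(1/nT + 1/(nC + nB)) = 2.2 × √(1/100 + 1/150) = 0.284
- Share borrowed: s = nB/(nC + nB) = 100/150 = 0.667
- Rate = Φ(−z + s × d/SE)

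| d | s × d/SE | Rate |
|---|---|---|
| −0.3 | −0.704 | 0.9% |
| 0 | 0 | 5.0% |
| 0.3 | 0.704 | 17.3% |

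The rate reaches 10% at d = (1.645 − 1.282) × 0.284/0.667 = 0.155 points. A simulation of 400,000 trials agreed with the formula at d = 0.3 (17.4% against 17.3%).

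**Placebo total fixed at 150, pooled.** SE stays at 0.284, so the rate at d = 0 is 5.0% whatever the split. At d = 0.3:

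| Concurrent / borrowed | s | Rate |
|---|---|---|
| 100 / 50 | 0.333 | 9.8% |
| 75 / 75 | 0.500 | 13.2% |
| 50 / 100 | 0.667 | 17.3% |
| 30 / 120 | 0.800 | 21.2% |

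**Hierarchical placebo borrowing.** Two donors of 50, with a half-normal prior of scale 0.25 or 0.5 on the between-study SD. The simulated rates are 1.3-1.7% at d = −0.3, 3.8-3.9% at d = 0 and 7.9-9.8% at d = 0.3. Here the rate at d = 0 does change with the split. With the total held at 150 it falls from about 4.5-4.7% with 100 concurrent to about 3.1-3.5% with 30. The constant 5.0% above is therefore a property of pooling only.

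**Hierarchical treatment-effect borrowing.** 100:50 per ISA, half-normal scales 0.25 to 1.0. With one donor the rate is 3.7-3.8% if the donor effect is 0 and 7.3-12.8% if it is −0.5. With two donors it is 2.9-3.1% and 9.9-19.7%.

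**No borrowing.** With nB = 0, s = 0 and d drops out of the formula.

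**Other unstated inputs.** The rate can depend on quantities outside the definition even without borrowing. Take a CSF of Pr(effect < −0.3) > 0.70 with 100:50 and z(0.70) = 0.524. The rate is Φ(−0.3/SE − 0.524), with SE = SD × √(1/100 + 1/50).

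- SD 2.0: SE = 0.346, rate 8.2%
- SD 2.5: SE = 0.433, rate 11.2%

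Section 9.2 does not list the SD as something to vary either, and that does not make the definition faulty. It is an input the simulation must set and defend.

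**The case for a change.** The strongest argument for a change is that the numbers are left to the ISAs but the definition is not: Section 9.2 fixes it for all of them. The duty to justify borrowing makes an ISA disclose its donor assumptions, not vary them. The protocol foresees shifts in placebo response by period and among repeat participants, yet does not carry them into its error rate. Under pooling, the no-difference value cannot show what is lost when concurrent placebo is replaced by borrowed placebo. One paragraph and some extra simulation runs would close the gap.

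Part of this stands. No text expressly asks for a placebo-difference scenario, and an ISA team would do well to run one. But the argument relies on the least demanding reading of a section that asks for the rate to be justified. Donor placebo means and donor effects must be given values before a borrowing design can be simulated at all, so they cannot be overlooked. The treatment differences that Section 9.2 wants varied can reasonably be read to include donor effects. At master-protocol level the donors, the method and the CSF are still unknown, so a prescribed grid could say little beyond asking for a plausible range.

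**Conclusion.** No change follows. The false positive rate of an ISA that borrows does depend on placebo differences and donor effects. Under the assumed inputs, a 0.3-point placebo difference takes it from 5.0% to about 17% with unadjusted pooling, and from about 4% to 8-10% with hierarchical borrowing; a difference the other way lowers it. None of these sizes belongs to this trial, and the largest come from the most sensitive of the six listed strategies.

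What remains is missing detail of a kind the protocol hands to its ISAs. Defining a false positive rate by a zero effect is standard practice, and the other quantities it depends on belong to the simulation. Added text in Section 9.2 would only list scenarios to be reported elsewhere; it would correct no rule, number or analysis stated in this document. An ISA that uses only its own data is unaffected. Whether a given ISA has explored these scenarios adequately can be judged only from that ISA and its SAP, which are not shown.
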